1.3 Clinical data

1.3.1 Human safety and tolerability data

S1P receptor modulators are known to cause dose dependent transient decrease in heart rate within 2-3 h of drug intake ([Legangneux et al 2013](#), [Hoch et al 2014](#)).

Commercially Confidential Information

As of 05-Mar-2018, approximately 3279 unique subjects have been enrolled into the siponimod clinical program (inclusive of Phase 1, Phase 2 and Phase 3), of which approximately 2742 unique subjects (912 healthy volunteers, 1787 patients with MS, 43 patients with PM or DM) have received siponimod and 925 subjects (297 healthy subjects and 628 patients) have received placebo. This includes subjects who sequentially received placebo and siponimod. In addition, 1 ICH patient has been enrolled in ongoing placebo-controlled study CBAF312X2207 (this study) and 363 subjects (all healthy volunteers) were exposed to other drugs.

The cumulative exposure of clinical trial subjects to siponimod since the Development International Birth Date (DIBD) of 05-Mar-2009 is estimated to be approximately 4840 patient-years. Healthy subjects have received siponimod as single doses or as multiple doses (single doses: 0.1 mg to 75 mg, multiple doses: 0.25 mg to 20 mg). Patients with MS have received siponimod (0.25 mg to 10 mg) daily from 1 day to 73 months during the clinical development program (please see Investigators Brochure).

The safety profile of BAF312 includes the following identified risks: transient effects on heart rate and rhythm (bradyarrhythmia and 2nd degree AV block) at treatment initiation that are completely avoided by initial up-titration; liver enzyme elevation; lymphopenia due to lymphocyte redistribution (main targeted PD effect of BAF312); seizures; hypertension; macular edema; and varicella zoster (VZV) infection reactivation.

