A placebo-controlled Phase II study of BAF312 in 297 patients with relapsing remitting MS (RRMS) showed significant dose-response relationship at Month 3. BAF312 treatment reduced the combined unique active lesion count by up to 80% vs. placebo, with the 2 mg dose providing near-maximal efficacy. Five transient symptomatic bradyarrhythmic events without sequelae were observed with the two highest doses (3/40 on 2 mg, and 2/50 on 10 mg) without titration. Serious adverse events (SAEs) included one death 27 days post-study drug discontinuation, likely due to previously unrecognized coronary artery disease. Other safety findings included liver enzyme elevations that were thought to be dose-related (4.3% of patients at higher dose

levels, 2 and 10 mg, had transaminases >3x upper limit of normal) and one case of macula edema in a patient with history of uveitis ([Selmaj et al 2013](#)), which has been recognized with longer-term BAF312 exposure.

The most common AEs were headache, bradycardia, dizziness and nasopharyngitis. A dose-dependent effect of BAF312 treatment on the occurrence of headache, bradycardia and dizziness reported as AEs was demonstrated. Common types of infections observed included nasopharyngitis, sinusitis, influenza and urinary tract infections, although no apparent treatment relationship was evident.

For more details, please see the Investigator's Brochure.

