3.7 Risks and benefits

The risk to patients in this trial must be minimized by compliance with the eligibility criteria and study procedures, close clinical monitoring, and clear instructions to the Investigator on how to manage symptomatic bradycardia if it occurs.

Bradycardic effect – Treatment initiation with BAF312 results in transient decrease in HR in a dose-dependent manner, with nadir ~3-4 h after the first dose. In a clinical study in MS patients (CBAF312A2201) without dose titration, five cases of second degree AV blocks were reported: 3/29 in the 2 mg group and 2/50 in the 10 mg group. Implementation of dose titration effectively mitigated the occurrence of bradycardic events. In this study, the dose is titrated to the target daily dose of CCI BAF312. The need to achieve fast therapeutic concentration was carefully weighed against the need to prevent bradycardic effects. Unlike ischemic stroke, in which reflex tachycardia and increased blood pressure is typically allowed to persist (to some extent) to maximize perfusion of the ischemic penumbra, in hemorrhagic stroke most supportive therapies are aimed at lowering blood pressure to minimize likelihood of acute expansion of the initial hematoma. Given this, transient bradycardia carries significantly less risk in the ICH patient population than in patients with ischemic stroke.

During the first 48 hours of treatment, all patients will be on continuous CV telemetry in Stroke Units/Neurointensive Care Units, and special attention will be given to the monitoring of the HR. In case of symptomatic bradycardia, the Investigator should follow the guidance given in [Section 6.6](#). Under those predefined conditions, BAF312 treatment must be interrupted. When the heart rate has recovered, the treatment may be started again, as judged by the Investigator.

Risk of infection - The core PD effect of BAF312 is dose-dependent reduction of peripheral lymphocyte counts to 20-30 % of baseline due to their sequestration in the lymphoid tissues. As a consequence, there is an increased risk of infections. Patients with low baseline lymphocyte count are excluded from the study. There were no reports of increased bacterial infections between drug and placebo in the MS population with S1P₁ modulators (fingolimod

and BAF312). Although the risk of infection is considered small given the short treatment duration of 14 days, in this critically-ill population this risk might be higher.

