11.5.2 Safety

Vital signs

All vital signs data will be listed by treatment group, patient, and visit/time and if ranges are available abnormalities (and relevant orthostatic changes) will be flagged. Summary statistics will be provided by treatment and visit/time.

ECG evaluations

All ECG data will be listed by treatment group, patient and visit/time, abnormalities will be flagged. Summary statistics will be provided by treatment and visit/time.

Clinical laboratory evaluations

All laboratory data will be listed by treatment group, patient, and visit/time and if normal ranges are available abnormalities will be flagged. Summary statistics will be provided by treatment and visit/time.

Adverse events

All information obtained on adverse events will be displayed by treatment group and subject.

The number and percentage of patients with adverse events will be tabulated by body system and preferred term with a breakdown by treatment. A patient with multiple adverse events within a body system is only counted once towards the total of this body system.

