**List of abbreviations**

AE	Adverse event
AESI	Adverse event of special interest
aPHE	absolute Perihematoma Edema
ATC	Anatomical Therapeutic Classification
AUC	Area Under the Curve
bid	bis in diem/twice a day
BMI	Body Mass Index
CSR	Clinical Study Report
CT	Computed Tomography
CTCAE	Common Terminology Criteria for Adverse Events
C-SSRS	Columbia-Suicide Severity Rating Scale
DBL	Database Lock
DMC	Data Monitoring Committee
ECG	Electrocardiogram
eCRF	Electronic Case Report Form
	Commercially Confidential Information
FAS	Full Analysis Set
FIR	First Interpretable Results
GCS	Glasgow Coma Scale
HLT	High level terms
i.v.	Intravenous
IA	Interim Analysis
ICH	Intracerebral hemorrhage
	Commercially Confidential Information
MedDRA	Medical Dictionary for Drug Regulatory Affairs
mRS	modified Rankin Scale
NF-L	Neurofilament light
NIBR	Novartis Institute for BioMedical Research
	Commercially Confidential Information
PAS	Pharmacokinetics Analysis Set
PDT	Programming Deliverables Tracker
PHE	Perihematoma Edema
PK	Pharmacokinetics
PPS	Per-Protocol Set
PT	Preferred Terms
p.o.	Oral
PRO	Patient-reported Outcomes
QD	Quaque die / once a day
RAP	Report and Analysis Process
	Commercially Confidential Information
SAE	Serious Adverse Event
SAP	Statistical Analysis Plan
SAS	Statistical Analysis System

SOPs	Standard Operating Procedures
SMQ	Standardized MedDRA Queries
SOC	System Organ Class
TFLs	Tables, Figures, Listings
	Commercially Confidential Information
WHO	World Health Organization

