**Adverse events (AEs)**

All information obtained (e.g. relatedness to study drug, action taken etc.) on adverse events will be displayed by treatment and patient. AEs will be coded using the latest version of MedDRA available at the time of clinical database lock.

AEs summarized will be all events recorded during the study. Any AE with a missing start date will be considered as starting in the study.

The number and percentage of subjects with adverse events will be tabulated by body system and preferred term with a breakdown by treatment. A patient with multiple AEs within a body system is only counted once towards the total of this body system.

The following AE summaries will be produced by treatment:

- AEs, regardless of study drug relationship by primary system organ class and preferred term
- AEs, regardless of study drug relationship by primary system organ class and preferred term and severity
- AEs, regardless of study drug relationship by primary system organ class and preferred term and maximum CTCAE grade (all grades and grade 3/4 )

- AEs, with suspected study drug relationship by primary system organ class and by preferred term
- Serious adverse events (SAEs), regardless of study drug relationship, by primary system organ class and preferred term
- SAEs, with suspected study drug relationship, by primary system organ class and preferred term
- AEs leading to study drug discontinuation, regardless of study drug relationship, by primary system organ class and preferred term
- AEs requiring dose adjustment or study-drug interruption, regardless of study drug relationship, by primary system organ class and preferred term
- AEs requiring additional therapy, regardless of study drug relationship, by primary system organ class and preferred term
- Non-serious AEs (ie, AEs excluding serious AEs), regardless of study drug relationship, by primary system organ class and preferred term

Fatal AEs suspected to be related to study treatment will be provided by SOC and PT.

- Fatal SAEs regardless of study drug relationship will be provided by SOC and PT.

AEs will be summarized by presenting the number and percentage of patients having at least one AE, and having at least one AE by system organ class and/or preferred, severity and relation to study drug by treatment arm.

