### **Other safety evaluations**

Not Applicable.

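### The visible adverse event tables stop at body system and preferred term, so a known risk spread over several terms, above all bradyarrhythmia/conduction, has no single by-arm incidence or confidence interval

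*SAP*

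**What the plan says.** **AE tables.** SAP 8.2, Adverse events (AEs): "The number and percentage of subjects with adverse events will be tabulated by body system and preferred term with a breakdown by treatment". Protocol 11.5.2 has the same rule. The individual summaries in SAP 8.2 cross these two levels with severity, grade, relatedness, seriousness or action taken. The registry tables and the death table use the same levels. A patient with several events in one body system counts once for that system. The entry for other safety evaluations reads "Not Applicable".

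**Intervals.** SAP 5.2.3 gives Clopper-Pearson 95% intervals for treatment-emergent and serious treatment-emergent AEs, overall and by severity. It names no individual risk.

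**Known risks.** Protocol 1.3.1 lists seven identified risks. The first is "transient effects on heart rate and rhythm (bradyarrhythmia and 2nd degree AV block) at treatment initiation". The others are liver enzyme elevation, lymphopenia, seizures, hypertension, macular edema and VZV reactivation. Protocol 3.7 adds that infection risk might be higher in this population.

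**Grouping tools.** The SAP abbreviation list includes "Adverse event of special interest", together with SMQ and HLT. No visible analysis uses them.

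**Measured data.** SAP 8.2 plans counts and proportions of patients passing ECG thresholds, including heart rate down by more than 25% to below 50 bpm, PR above 220 ms, and PR up by more than 25% to above 220 ms. It also plans laboratory shift tables by parameter and arm. Telemetry abnormalities go to the AE page and get no listing of their own.

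**The concern.** Assessing the safety profile in ICH is a secondary objective, and bradyarrhythmia is the risk behind the i.v. titration and the 48 hours of cardiac monitoring. If its events are coded as, say, bradycardia, AV block, sinus pause and a low heart rate entered as a test finding, the by-arm comparison shows several sparse rows, possibly in more than one body system.

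Adding the rows can count a patient twice, and a body-system total mixes in unrelated cardiac events. With about 33 patients per arm, an excess can then look like scattered single cases. A grouping chosen after unblinding would be open to the charge that the terms were picked to fit the data.

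**Working it through.** The plan states no figure on this point to reproduce. The check has three steps.

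**1. What the visible text gives by arm for each identified risk**

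| Risk (Protocol 1.3.1) | By-arm output outside AE terms (SAP 8.2) | AE output |
|---|---|---|
| Bradyarrhythmia / AV block | Counts over heart-rate and PR thresholds | Separate preferred terms; second-degree block and sinus pauses appear only here |
| Liver enzymes | Shift table on normal ranges; Table 8-2 criteria get graphs and a listing, with no by-arm count stated | Preferred terms |
| Lymphopenia | Shift table | Preferred terms |
| Hypertension | Blood pressure summaries; notable values flagged in a listing | Preferred terms |
| Seizures | None | Preferred terms |
| Macular edema | None | Own row if coded to one term |
| VZV reactivation | None | Preferred terms, within the infection body-system total |

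A by-arm patient count from measured data is planned for 3 of 7 risks (heart rate/conduction, lymphocytes, liver enzymes). A predefined grouped AE incidence is visible for 0 of 7.

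The ECG counts only partly cover the first row. Scheduled ECGs are at baseline, Days 1 to 3 and Day 7. Unscheduled ECGs also enter abnormality analyses under SAP 4.4, but continuous monitoring does not, and none of the listed thresholds is a second-degree block, a pause or a symptom.

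**2. Why rows cannot simply be added**

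Suppose three preferred-term rows each show 1 of 33 BAF312 patients. The number of distinct patients is then 1, 2 or 3, and the rows do not say which. The Clopper-Pearson 95% intervals (beta quantiles at 0.025 and 0.975) are:

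- 1/33 = 3.0% (0.1% to 15.8%)
- 2/33 = 6.1% (0.7% to 20.2%)
- 3/33 = 9.1% (1.9% to 24.3%)

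**3. Illustration of lost visibility**

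Input from the documents: 33 per arm (SAP 1.4). Assumed: incidences p_B (BAF312) and p_P (placebo), one term per affected patient, and the split over k terms.

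Grouped row: P(X_B − X_P ≥ 4), with X_B ~ Bin(33, p_B) and X_P ~ Bin(33, p_P), summed exactly. Largest single-term row: P(max over j of (X_Bj − X_Pj) ≥ 4), with term probabilities p/k, from 1,000,000 simulated trials.

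| p_B vs p_P | Grouped | 2 equal terms | 3 equal terms | 4 equal terms | 80/10/10 split |
|---|---|---|---|---|---|
| 18% vs 3% | 72% | 47% | 29% | 19% | 57% |
| 10% vs 3% | 26% | 11% | 5% | 3% | 17% |
| 5% vs 3% | 4% | 1% | 0.5% | 0.2% | 2% |

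For scale, the protocol's own figures without titration are 3/40 = 7.5% or 3/29 = 10.3% at 2 mg, and 2/50 = 4.0% at 10 mg. The 18% row is above all of these, and the documents give no rate under titration.

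**Side finding.** Protocol 1.3.1 says "Five transient symptomatic bradyarrhythmic events without sequelae were observed with the two highest doses" and gives 3/40 at 2 mg. Protocol 3.7 says "five cases of second degree AV blocks were reported" and gives 3/29. These appear to be the same five events, with different labels and different 2 mg denominators. The two passages must be reconciled.

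**The case against.** A reader might infer that no by-arm incidence is planned for any known risk. The documents do not support that. The ECG threshold counts use treatment-arm denominators (SAP 4.2). The shift tables cover lymphocytes and liver enzymes whether or not an AE was entered. Infections should have a once-per-patient body-system total, and a single-term risk such as macular edema has its own row. This stands, and it confines the point to multi-term risks.

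A reader might also infer that the sponsor planned no grouping at all. That cannot be shown. The interim/DMC section, the section before section 10 and the SAS appendix are redacted, and output specifications sit in separate documents (SAP 1.1). The unused abbreviations fit either a redacted analysis or template text. What can be said is that the AE section, which is legible, refers to no grouping.

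The illustration is also open to challenge. Its rates are assumed, an even split is unfavourable to the plan, and Protocol 6.6 expects titration to remove nearly all such events. At 5% vs 3% even a grouped row shows little. That stands, so the result is given as a range. The two descriptions of the MS study show that labels vary, but they are not evidence of how MedDRA coding will fall in this trial.

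Finally, safety is declared descriptive, and all AEs are listed by patient, so terms could be combined by hand. With 33 per arm that is feasible. Done after unblinding, however, it leaves the choice of terms open, and it gives no planned interval.

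**Conclusion.** The point holds for risks spread over several preferred terms. The visible plan gives no once-per-patient, by-arm incidence or interval for bradyarrhythmia/conduction as a clinical event, and the ECG thresholds do not replace it. Seizure, hypertension and VZV reactivation are affected if they are coded to more than one term. For liver enzymes the shift tables are there, but the Table 8-2 criteria have no stated by-arm count.

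The size depends on unknown rates and coding. For an excess of at least 4 patients, three equal terms cut the chance of seeing it from 26% to 5% (10% vs 3%) or from 72% to 29% (18% vs 3%). An uneven split costs less.

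The primary analysis is untouched. The change is worth making because safety is a secondary objective and the remedy is cheap. It rests on the visible text only and lapses if a redacted section already defines the groups.

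**What to change.** Add one by-arm table to SAP 8.2, each patient counted once per risk, with n, % and the Clopper-Pearson 95% interval already used in SAP 5.2.3.

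- **Rows:** bradyarrhythmia/conduction first, then seizure, hypertension and liver enzyme elevation, with VZV reactivation shown separately.
- **Liver:** add a by-arm count of patients meeting each Table 8-2 criterion.
- **Definition:** a preferred-term list or SMQ for each row, frozen on blinded data before database lock. State whether the table counts treatment-emergent events (SAP 5.2.3) or all recorded events (SAP 8.2).
- **Keep** the body-system and preferred-term tables.
- If a redacted section already defines such groups, a cross-reference in 8.2 is enough.
- Separately, reconcile the 3/40 and 3/29 figures, and the event labels, in Protocol 1.3.1 and 3.7.

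The cost is some SAP wording, a term list agreed before lock and one extra table. Grouped rows will take in some non-specific terms, which stay visible in the retained tables. No clinical rule changes.

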### **Deaths**

Deaths will be summarized by primary system organ class and preferred term by treatment. Listing of all death will be produced for patient who signed informed consent and randomized.

### **Other safety evaluations**

Not Applicable.

### **Immunogenicity**

All immunogenicity results will be listed by subject and visit/time.

## **8.3 Graphical presentation**

Boxplots to visualize trends in longitudinal safety data (vitals, ECG, lab parameter) will be presented. An evaluation of Drug Induced Serious Hepatotoxicity (eDISH) plot will also be presented.

## Commercially Confidential Information

### **10 Sample size consideration**

The detailed sample size calculation of primary and secondary endpoint provided in protocol section 11.7.

**12 Appendix**

**12.1 SAS code**

Commercially Confidential Information

Commercially Confidential Information

Commercially Confidential Information

Commercially Confidential Information

## 12.2 Definition of benefit for individual endpoints

Measurement	Endpoint	Direction of benefit*
Questionnaire	mRS	Decrease

Commercially Confidential Information

Computed tomography scan	HV	Decrease
--------------------------	----	----------

\* In the direction of

Personal Protected Data
